## Adverse Events

In addition to RM complications (see above), any perioperative adverse event will be recorded, such as laryngospasm, bronchospasm, pneumothorax, subcutaneous emphysema, hypotension, bradycardia, desaturation ( $\text{SPO}_2 < 92\%$ ) or hypercapnia ( $\text{PaCO}_2 > 45 \text{ mmHg}$ ).

## Patient Records

For each patient we will have 4 data files

1. Demographic, intra- and post-operative patient data (Appendix 3)
2. Mechanical Ventilation data (Appendix 4)
3. Hemodynamic data (Appendix 5)
4. Blood Gas data (Appendix 6)

## Blinding Procedure

This will be a Double-blind clinical study. Patients will not be aware of ventilation strategy during the operation. The only un-blind person will be the Principal Investigator (PI). After the RM (or not), at T4 point time (see below), a Second Investigator (SI) will come into the operating room and will record measurements from monitor. The same person will also perform blood gas analyses on the specified time points and postoperative records in PACU. The measurements will be recorded in special files for each separate patient with patient id number and then will be entered in a SPSS data file (SPSS version 22) and will be analyzed. Analysis will be performed by the two investigators separately (the PI will be un-blind) and results should be matched.

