### Brief description

This will be an Interventional, Prevention, Parallel Assignment, Double-blind (patient, care-giver, outcomes Assessor), Randomized, Safety / Efficacy Study. We will use two parallel groups of children aged 1-14 years who are scheduled for elective Abdominal Laparoscopy

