## Randomization

In order to perform Randomization, the investigators will use web-software-generated blocks (available at: <http://www.randomization.com/>). Patients will be randomized to one of the two Ventilation Management Groups (RM or Control group) with 15 patients per group. Each patient assigned to participate in the study will have a sequentially numbered (from 1 to 30) sealed envelope containing Randomization Code (A or B). The Principal Investigator will be the only person who will be aware of the correspondence between Codes and study Groups. The envelopes will be concealed until deflation of pneumoperitoneum, just prior to application of RM (or not). All operations will be performed by the same team of surgeons and by the same anesthesiologists (PI and Second Investigator). In Appendix 1, there is an example of performed permuted blocks randomization with 30 patients, created by this web-software.

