## Time points of measurements

After a stabilization period of 1-2 minutes of Mechanical Ventilation (stabilization defined as a stable Vt for at least 4 consecutive breaths), the above parameters (except Blood gas measurements – see Appendix 6) will be measured at the following time points:

T1	Baseline	After tracheal intubation and ventilation stabilization, with the patient in the supine position and before surgical incision
T2	Pneumoperitoneum	After insufflating CO 2 to the defined IAP
T2c	Correction	After adjusting PIP to return Vt to 6-7 ml/kg IBW or within 10% of baseline
T3	Trendelemburg	After Trendelemburg positioning
T3c	Correction	After Trendelemburg positioning and after adjusting PIP to return Vt to 6-7 ml/kg IBW or within 10% of baseline
T4	Deflation	After completing the laparoscopic procedure with the patient returned to the supine position with the abdomen deflated
T4c	Correction	Post-deflation correction, after returning PIP to baseline
T5	After RM / Before Reversal of Neuromuscular Blockade	3 minutes after RM in the RM group and before the reversal of neuromuscular blockade and Extubation in both groups
T6	Post-operative	30 min after the admission in PACU

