## End of Treatment

The treatment (RM) will start 3 minutes after the Pneumoperitoneum deflation and will last for 30 seconds.

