## Appendix 1 - Permuted Blocks Randomization

30 subjects randomized into 5 blocks

A Randomization Plan  
from  
<http://www.randomization.com>

1. RM Group \_\_\_\_\_
2. RM Group \_\_\_\_\_
3. Control Group \_\_\_\_\_
4. Control Group \_\_\_\_\_
5. Control Group \_\_\_\_\_
6. RM Group \_\_\_\_\_
7. Control Group \_\_\_\_\_
8. Control Group \_\_\_\_\_
9. RM Group \_\_\_\_\_
10. RM Group \_\_\_\_\_
11. Control Group \_\_\_\_\_
12. RM Group \_\_\_\_\_
13. Control Group \_\_\_\_\_
14. RM Group \_\_\_\_\_
15. RM Group \_\_\_\_\_
16. Control Group \_\_\_\_\_
17. RM Group \_\_\_\_\_
18. Control Group \_\_\_\_\_
19. RM Group \_\_\_\_\_
20. RM Group \_\_\_\_\_
21. RM Group \_\_\_\_\_
22. Control Group \_\_\_\_\_
23. Control Group \_\_\_\_\_
24. Control Group \_\_\_\_\_
25. RM Group \_\_\_\_\_
26. Control Group \_\_\_\_\_
27. RM Group \_\_\_\_\_
28. Control Group \_\_\_\_\_
29. Control Group \_\_\_\_\_
30. RM Group \_\_\_\_\_

30 subjects randomized into 5 blocks  
To reproduce this plan, use the seed 26464  
Randomization plan created on 9/18/2017, 11:44:26 PM

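### The blinded assessor is said to enter both after the recruitment manoeuvre and at T4, which precedes it, and is also a treating anaesthetist, so the T5 compliance reading could be unblinded

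*Protocol*

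**What the plan says.** The Brief description declares the trial "Double-blind (patient, care-giver, outcomes Assessor". The Blinding Procedure section makes the Principal Investigator (PI) the only unblinded person and assigns the monitor readings to the Second Investigator (SI): "After the RM (or not), at T4 point time (see below), a Second Investigator (SI) will come into the operating room". The SI also performs the blood gas analyses and keeps the PACU records.

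The table of measurement time points defines T4 as "After completing the laparoscopic procedure with the patient returned to the supine position with the abdomen deflated". T4c follows, and then T5: "3 minutes after RM in the RM group and before the reversal of neuromuscular blockade and Extubation in both groups". End of Treatment fixes the manoeuvre: "The treatment (RM) will start 3 minutes after the Pneumoperitoneum deflation and will last for 30 seconds". Under Randomization, the envelope stays closed until deflation, just before the RM is given or omitted. The same section says: "All operations will be performed by the same team of surgeons and by the same anesthesiologists (PI and Second Investigator".

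On the analysis, the Blinding Procedure section says: "Analysis will be performed by the two investigators separately (the PI will be un-blind) and results should be matched". Appendix 1 shows a list headed "30 subjects randomized into 5 blocks", which the Randomization section describes as an example.

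**The concern.** Assessor blinding depends on when the SI is in the room, and the protocol gives incompatible answers. An assessor present from T4 onwards sees the switch to manual mode and the 30-second inflation, or sees that neither happens. Either one reveals the arm before T5. By Appendix 4, T5 is the only compliance reading taken after the RM, so it carries the primary comparison.

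Knowing the arm matters because the Baseline Ventilation Strategy section has ventilatory values copied by hand from the screen. T5 is tied to the RM only in the RM group. For controls, the sole condition is that it comes before reversal and extubation, so the recorder has some choice of moment. A reading taken with knowledge of the arm cannot be re-blinded afterwards, so the question has to be settled before the first patient.

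**Working it through.** The core of the check is time order, taken from the protocol's own definitions.

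1. Deflation, patient supine: T4 (minute 0 for this purpose).
2. Peak pressure returned to baseline: T4c, before the RM.
3. RM starts at 3 minutes and ends at 3 + 0.5 = 3.5 minutes.
4. T5 in the RM group is 3 minutes after the RM: 3 + 3 = 6 minutes if counted from its start, 3.5 + 3 = 6.5 minutes if counted from its end. The protocol does not say which.
5. T5 in the control group has no stated minute.

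T4 therefore comes before the RM, and an entry at T4 cannot also be an entry after the RM. A genuinely later entry is possible: the gap between the end of the RM and T5 is 6 − 3.5 = 2.5 to 6.5 − 3.5 = 3 minutes.

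Next, the roles. One of two anaesthesiologists for all operations is not someone who first comes in after the RM. Reading T4 as a slip for T5 repairs the timing but leaves this conflict. Separately, the PI gives anaesthesia and is unblinded, so a care-giver is unblinded on any reading of the entry time.

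Size of a possible bias: the documents give none, so what follows is an assumption shown over a range. The plan's own figure reproduces first. With a standardised effect of 0.2/0.15 = 1.33, two-sided alpha 0.05 and power 0.90, the noncentral t calculation gives 12.86, hence 13 per group as stated. Now take 15 per group, the plan's SD of 15% of the mean, no true effect, and a systematic reading bias b between groups. The noncentrality is (b/0.15) × √(15/2), with 28 degrees of freedom.

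- b = 2% of the mean: noncentrality 0.365, type I error about 0.064
- b = 5%: 0.913, about 0.143
- b = 10%: 1.826, about 0.422

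These show sensitivity only. Nothing in the protocol says that a bias of any such size would occur.

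Predictability of the list is secondary and conditional. Every consecutive six in Appendix 1 is 3:3. Someone who knows the earlier allocations in such a block can foresee the final run of identical ones. The chance that this run has length at least 1, 2 or 3 is 2 × C(5,3)/20 = 1, 2 × C(4,3)/20 = 0.4 and 2 × C(3,3)/20 = 0.1. The mean is 1 + 0.4 + 0.1 = 1.5 per block, or 5 × 1.5 = 7.5 of 30 (25%). In the printed example the final runs are 1, 1, 1, 3 and 1, which makes 7 of 30.

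**The case against.** The strongest reply is that the sentence on the SI's entry says after the RM just as plainly as it says T4. If T4 is a slip for T5, the reading can be blinded. A reader might infer that the primary outcome will be read unblinded in all patients, because seeing the RM identifies 15 and its absence the other 15. The documents do not support that: it applies one half of a self-contradictory sentence and ignores the other. What stands is that the reading could be unblinded, and that the SI's anaesthetist role points the same way independently of T4.

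The scope for bias is also limited. The workstation computes compliance, a stable tidal volume is required before each reading, and T5 is timed in the RM group. Ventilator adjustments belong to the anaesthesia team, which includes the unblinded PI, so a different recorder would not remove that route. Hand transcription and the untimed control T5 remain.

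Three further inferences fail or need a condition:

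- A reader might think that seeing one RM decodes the trial through the fixed A/B codes. Records carry patient ID numbers, and the protocol does not show that the SI sees a patient's code while recording.
- The 25% figure holds only if the live list is built like the example. Exclusions between induction and deflation rest mostly on named clinical events or surgical conversion, so the PI's room to act on a foreseen allocation is small, though not nil.
- The PI's unblinded analysis is not the only one. The same sentence provides a separate analysis by the second investigator and a match of results.

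**Conclusion.** The assessor blinding cannot be carried out as written. The entry time contradicts the time-point table and the start of the RM, and the SI's role contradicts the entry. The care-giver label conflicts with an unblinded treating PI. If T4 or the anaesthetist role is followed, the only post-RM compliance reading could be taken by someone who has seen the arm. The likely bias cannot be quantified from the documents. It is limited by automatic computation and left open by manual copying and the untimed control T5.

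The entry time, the SI's role and the control T5 should be settled before enrolment. The masking label is a simple correction. The block-size point is lesser and rests on the live list following the Appendix 1 structure. An unblinded operator is unavoidable in this design and is not itself a fault.

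**What to change.** Reconcile the Blinding Procedure, Time points of measurements, End of Treatment, Randomization and Brief description sections so that they state:

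- T1 to T4c are recorded before the envelope is opened.
- The SI is out of the room from envelope opening until the RM window has clearly ended, enters at the same time after deflation in both groups, and records T5 and T6. Entry at exactly 3.5 minutes leaves no margin, so the time should fall later within the gap before T5.
- Control T5 is taken at the same time after deflation as T5 in the RM group, with the reference point (start or end of the RM) stated.
- The SI does not give anaesthesia during the RM window. The PI, already unblinded, is present.
- The SI's masked primary analysis is completed before the PI's unblinded one.
- The trial is described as patient- and assessor-blind.

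As a secondary step, generate the live list with varying block sizes that are not disclosed.

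The cost is protocol wording and a new list, plus a short period in which the PI alone covers anaesthesia. The site must confirm that this is feasible. If it is not, someone other than the SI has to take the T5 reading, or the claim of assessor blinding has to be dropped.

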### Statistical Analysis

[figure not shown]
Investigators will assess data for normality (using Kolmogorov Smirnov and Shapiro Wilks test). Ventilatory and hemodynamic data and intraoperative and postoperative variables (all continuous variables) will be presented as mean values (+/- SD). Data will be compared between and within groups using Mixed Analysis of Variance (Mixed Anova - General Linear Model) if are normally distributed or with Kruskal Wallis test in case that we do not have normally distributed data. Bonferroni correction will be used for multiple comparisons correction. In order to check and supplement our Mixed Analysis of Variance we will also use two-sample t-test to compare the two groups at each time point (for ventilatory and hemodynamic variables). Patient and procedural characteristics will be compared between groups using independent-sample t-test for continuous variables and chi-square test for categorical variables. Two tailed P-values < 0.05 will be considered statistically significant. For data analysis, the investigators will use SPSS statistical software (version 22).

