## Data Presentation Plan

### Flow chart

Supposing the number of eligible children is  $k$  and the number of excluded children before randomization is  $e$ , with possible reasons for exclusion ( $e_1, e_2, e_3$ ), trial flow chart is shaped as below.

Finally, 30 patients will be randomized in two groups.

If the great majority of the patients will complete the study, we will use a Per Protocol analysis. If many of the randomized patients will not complete the study, we will use an Intention to Treat analysis of data (ITT). According to ITT analysis of data, we will use all the data of all the randomized patients regardless of whether they completed the trial or not. For the missing values we will use the Last Observation Carried Forward (LOCF) approach.

Patient demographics should be similar between the two groups (Table 1). If not, differences will be mentioned and this will be a major limitation of our study.

Intraoperative characteristics (anesthesia duration, pneumoperitoneum duration, IAP, blood loss, administration of crystalloids and / or blood products and intraoperative use of vasoconstrictors should be similar between the two groups (Table 1).

The length of hospital stay and the possible differences between the two groups should be mentioned (Table 1). The number of patients that will develop postoperative pulmonary complications (mainly pneumonia, diagnosed with clinical evaluation and chest radiogram) and possible differences between the two groups should also be recorded.

Pneumothorax and pneumomediastinum would be serious complications, which could have a strong relationship with the RM manipulation, and should be also recorded (see adverse event section above)

**Table 1.** Patient demographics presented as mean (SD) or n = number of patients. Intra- post-operative events presented as mean (SD)

	RM group (n = 15)	Control group (n =15)
Patient Demographics		
Age (years) [mean (SD)]		
ASA (n) [mean (SD)]		
Weight (grams)		
Height (m)		
BMI (kg/m  )		
Sex (male / female)		
Intraoperative characteristics		
Duration of Anesthesia (min)		
Duration of Pneumoperitoneum (min)		
IAP (mmHg)		
Crystalloids (ml)		
Blood (units)		
Need for Vasoconstrictor drugs (n)		
Postoperative characteristics		
Length of Hospital stay (days)		
Pulmonary Complications (n)		
Pneumothorax (n)		
Pneumomediastinum (n)		
Pneumonia (n)		
Other (n)		

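### The un-blind principal investigator runs one of two unranked analyses, and the per-protocol/ITT choice has no numerical trigger, so it can be made after group results are known

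*Protocol*

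**What the plan says.** **Who analyses.** The Blinding Procedure section calls the trial double-blind, with the PI as the one un-blind person. It then states: "Analysis will be performed by the two investigators separately (the PI will be un-blind) and results should be matched". The Randomization section confirms who holds the key: "The Principal Investigator will be the only person who will be aware of the correspondence between Codes and study Groups".

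**Which patients are analysed.** The Flow chart section says: "If the great majority of the patients will complete the study, we will use a Per Protocol analysis". If many randomized patients do not complete, ITT is used instead, and "For the missing values we will use the Last Observation Carried Forward (LOCF) approach". Neither condition has a number.

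**Which test.** The Statistical Analysis section uses a Mixed ANOVA if the data are normally distributed, "or with Kruskal Wallis test in case that we do not have normally distributed data". Normality is assessed with two tests. Bonferroni correction is named, and t-tests at each time point are a supplement.

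**Which variable.** The Primary endpoint section defines both raw and weight-corrected dynamic compliance. The Efficacy and Safety Issues section sets the 20% criterion for the RM group on the weight-corrected mean, then gives a second 20% criterion, for the change from baseline within that group, without weight correction.

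**Whether the second analyst is blinded.** The Randomization section says: "All operations will be performed by the same team of surgeons and by the same anesthesiologists (PI and Second Investigator". The Blinding Procedure section has the second investigator come into theatre only after the RM, at T4. In Time points of measurements, T4 is deflation, T4c follows it, and T5 is 3 minutes after the RM. End of Treatment starts the RM 3 minutes after deflation, so T4 comes before the RM.

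**The concern.** Two independent analyses, one of them blinded, are a useful safeguard if the blinded one decides. Here the protocol does not rank them. If they differ because of an analytic choice and not a computing slip, someone who knows the allocation takes part in settling the difference.

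That matters because one influential choice is written so that it can be settled late. The set of patients analysed depends on a description of completeness that reasonable people could apply either way. The plan's own drop-out assumption falls in that grey zone: 15% of 30 is 4.5 patients, so about 26 of 30 (87%) would complete. Nothing in the protocol requires the set to be declared before group results are known.

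The choice may also not be neutral between arms. Efficacy and Safety Issues says that patients with severe hemodynamic instability will be removed from the study, and instability caused by the RM can arise only in the RM arm.

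At stake are the error rate of the primary comparison and the credibility of the double-blind label at the analysis stage.

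**Working it through.** **1. The plan's own figure.** No stated number is disputed here, but the design reproduces. With d = 0.20/0.15 = 1.33 and two-sided alpha 0.05, power comes from the noncentral t with 2n − 2 degrees of freedom and noncentrality d√(n/2). At n = 13 the noncentrality is 1.333 × √6.5 = 3.40. Power is 0.877 at 12 per group and 0.903 at 13, so 13 per group (26 in all) is correct. Fixing the analysis choices in advance does not change it.

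**2. What an open choice of analysis set can do.** Null simulation, 4,000 trials per scenario.

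- From the protocol: 15 per arm, SD 15% of the mean, two-sided 0.05, LOCF under ITT.
- Assumed: 2, 4 or 6 of 30 missing T5 at random; T4c–T5 correlation ρ of 0.5 or 0.8; a t-test at T5 in place of the Mixed ANOVA; every patient missing T5 has a T4c value.
- Model, with no group effect: T4c = 1 + 0.15b and T5 = 1 + 0.15(ρb + √(1 − ρ²)e), where b and e are independent standard normal.
- Per protocol uses observed T5 only. ITT/LOCF replaces a missing T5 by T4c. The steered result is the smaller of the two p-values.

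| Missing of 30 | ρ | One fixed analysis | Smaller p of the two sets |
|---|---|---|---|
| 2 | 0.5 | 4.9% | 6.2% |
| 2 | 0.8 | 5.3% | 6.2% |
| 4 | 0.5 | 5.1% | 6.9% |
| 4 | 0.8 | 4.8% | 6.5% |
| 6 | 0.5 | 5.8% | 8.3% |
| 6 | 0.8 | 5.2% | 7.5% |

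The Monte Carlo standard error near 5% is √(0.05 × 0.95/4000) = 0.34 percentage points.

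**3. With the normality rule followed.** The protocol gives no cut-off, so a Shapiro-Wilk test at 0.05 is assumed to decide between the t-test and Kruskal-Wallis. With a single analysis set, this rule leaves the false-positive rate at about 5% to 6%. With the choice of set added and 2 or 4 missing, simulations gave 5.9% to 8.0%, that is, about 6% to 8%.

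**4. The blinding statements side by side.** If the second investigator is an anesthesiologist throughout every operation, that person is present when the RM is given or withheld. If the second investigator enters at T4, entry precedes the RM. Only entry after the RM keeps this analyst blinded, and that does not fit the T4 label. The statements cannot all hold.

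**The case against.** **Matching may be only a concordance check.** The analyses are run separately, and agreement may simply be how computing errors are caught. That is a fair reading. A reader might infer that the blinded result is to be moved toward the un-blind one, but the text does not say so. What stands is that nothing limits the PI's run to checking and nothing says which result prevails.

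**A statistical analysis plan may settle this.** Discrepancy rules and sign-off dates often sit there. The parallel un-blind analysis and the unquantified trigger for the analysis set, however, are stated in this protocol, so they are badly fixed here and not merely left for later.

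**The test is not a free choice.** A reader might count the smaller p of t-test and Kruskal-Wallis as an allowed route. It is not: normality decides, and taking the smaller p would break the rule. The missing cut-off and tie-break leave some room, but little.

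**Larger inflation figures can be produced.** In the same simulation (SD of log weight assumed to be 0.6), adding the smaller p of the two tests and raw versus weight-corrected compliance gives 14.5% to 16.7%. Adding change from T4c gives 19.4% to 22.7%. The documents do not support these as the size of this problem. Change from T4c is not a listed alternative to the Mixed ANOVA, and the choice of compliance variable is a separate question of endpoint definition.

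**The stated trigger is completion, not the result.** True. Inflation arises only if someone uses the vagueness, and the protocol gives no sign that anyone intends to.

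**Conclusion.** The point holds in a limited form. The only person who knows the allocation runs an analysis that is not ranked below the blinded one, no rule resolves a disagreement, and the choice of analysis set has no number and no required date. The documents also conflict on whether the second analyst is blinded, so the safeguard itself is uncertain.

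The supported size is a false-positive rate of about 6% to 8% against 5%. This is an illustrative worst case in which the favourable set is always taken. It rests on 2 to 4 of 30 missing at random, a T4c–T5 correlation of 0.5 to 0.8, and a T5 t-test in place of the Mixed ANOVA with Bonferroni correction. Patients excluded before deflation may have no T4c value, and removals confined to the RM arm would not be missing at random; neither was modelled.

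This is a cheap improvement. It does not invalidate the design or suggest that results will be steered.

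**What to change.** - State that the reported analysis is the one run by the blinded investigator on data coded A/B.
- Fix and sign the analysis set (one named set, or a numerical completion threshold), the primary compliance variable and the test, including the normality criterion, before the code is broken. Best is before A is compared with B at all, because a two-sided p-value is the same whichever label is the RM group. The PI, who knows the code throughout, should not take part in these decisions.
- State that the PI's un-blind run is a later computing check. A mismatch is traced to its computing cause, and the check cannot change the signed choices.
- Reconcile Randomization, Time points of measurements and Blinding Procedure on where the second investigator is during the operation and at which time point that person enters, so that this analyst is in fact blinded.

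**Cost.** Protocol wording only. Both analysts and the A/B codes already exist, and the sample size stays at 26, with 30 randomized. One fixed analysis keeps the error rate at about 5% (4.8% to 5.8% in the simulation). The downside is that the PI sees results slightly later.
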